Pembrolizumab is to be administered as an IV infusion over 30 minutes in a dose of 200 mg Q3W, for up to 1 year for as long as patients are deriving clinical benefit (ie, objective response or SD) and tolerating therapy well.

Reference Therapy, Dosage, Duration, and Mode of Administration: None

**Duration of Study:** This study consists of a 28-day screening period, treatment period, and 30-day post-treatment follow-up. The treatment period consists of at least five 3-week cycles that can repeat for up to 1 year.

**Efficacy Endpoints:** The primary efficacy endpoint is the rate of new or improved antitumor response after the addition of ALKS 4230 treatment in patients receiving ongoing anti-PD-1 therapy but who have not achieved a CR.

The secondary efficacy endpoints in this study include:

- 1. Duration of response, progression-free survival, time to progression, rate of non-progression at 6 months, and OS
- 2. Antitumor response rate of subsets of patients based on disease status (PR, SD, or PD) at

screening

3. Antitumor activity as measured by radiological assessment compared to screening

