#### Protocol ION-01-ALKS4230

PBMC=peripheral blood mononuclear cell; PT=prothrombin time; Q3W=every 3 weeks; RECIST=Response Evaluation Criteria in Solid Tumors; SAE=serious adverse event; TMB=tumor mutational burden; Trp=tryptophan; TSH=thyroid-stimulating hormone; Tx=treatment; w=Week (visit).

- a In general, assessments/procedures are to be performed on Day 1 and prior to the first dose of treatment for each cycle unless otherwise specified. Treatment cycles are 3 weeks; however, the treatment cycle interval may be increased due to toxicity according to the dose modification guidelines provided in Section 9.1.1 and Section 9.1.2.
- b In patients who discontinue study therapy, every effort should be made to continue monitoring their disease status by radiologic imaging per local standard of care or Investigator clinical judgment every 8 weeks for up to 2 years until (1) the initiation of new therapy, (2) death, or (3) the end of the study, whichever occurs first.
- c After the start of new anticancer treatment or documented disease progression by local imaging review, the patient should be contacted by telephone every 12 weeks ( $\pm 1$  week) to assess for survival status for up to 2 years.
- d In general, the window for each visit is -1/+3 days unless otherwise noted. Pembrolizumab is given on Day 1 of each cycle with a -1/+3-day window. ALKS 4230 is given daily on 5 consecutive days on Days 1 through 5 of the first week of each 3-week treatment cycle. Day 1 of each 5-day dosing period will have a -1/+3-day scheduling window; however, all subsequent days within a cycle (Days 2 to 5) must be administered on their scheduled day. Refer to Section 9.5.2 for management of skipped dosing days.
- e Written consent must be obtained prior to performing any protocol-specified procedure. Consent should include option to copy relevant imaging for central review by the manufacturer, enabling confirmation of Investigator-determined responses. Results of a test performed prior to the patient signing consent as part of routine clinical management are acceptable in lieu of a screening test if performed within the specified time frame (eg, within 28 days prior to the first dose of study drug). A patient ID number will be assigned when the patient is enrolled.

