- v The post-treatment (second) biopsy will be performed on the same or similar tumor site during the first cycle of therapy at C1D12, or at any time from C1D8 through C1D19.
- w Fecal swab/storage devices and instructions must be given to the patient; sample collection to be performed at home by patient and returned to clinical research site at the next study visit.
- x Additional information regarding correlative studies is located in Table 16, and additional instructions are provided in the Laboratory Manual.

Patient Group	Imaging	Follow-up	AE Tracking
Patients with SD/PR who continue on Tx, no progression, for up to 1 year	9 weeks post-treatment start (within 7 days prior to Cycle 4), then within 7 days prior to every 3 rd cycle Follow-up: every 12 weeks ±1 week	Safety Follow-up Visit at 30 days after discontinuation Clinic visit every 8 weeks	Until 90 days after discontinuation or 30 days after discontinuation if patient begins new anticancer therapy
Patients who progress on-study before 1 year	Per local standard of care	Safety Follow-up Visit at 30 days after discontinuation or before start of new therapy, if applicable (in- clinic) Safety Follow-up Visit at 90 days after discontinuation (in-clinic preferable, by phone possible) Survival telephone call every 12 weeks for up to 2 years	Until 90 days after discontinuation or 30 days after discontinuation if patient begins new anticancer therapy
Patients who discontinue treatment due to any reason other than progression	Per local standard of care or Investigator clinical judgment	Safety Follow-up Visit at 30 days after discontinuation or before start of new therapy, if applicable Clinic follow-up until toxicity resolves or until death	Until 90 days after discontinuation or 30 days after discontinuation if patient begins new anticancer therapy
Patients who achieve CR on Tx (after at least 24 weeks of Tx + 2 doses post-CR imaging)	After discontinuation of treatment: Follow-up: every 12 weeks ±1 week OR at clinical signs/symptoms of progression	Safety Follow-up Visit at 30 days after discontinuation Clinic visit every 8 weeks	Until 90 days after discontinuation or 30 days after discontinuation if patient begins new anticancer therapy

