#### 9.5.2. Dose Interruptions and Stopping Rules

[figure not shown]
In consideration of the prescribing information for pembrolizumab (Keytruda USPI), follow the label accordingly for pembrolizumab dose adjustments and stopping rules. If a patient permanently discontinues study therapy, the patient should be discontinued from the study; however, every effort should be made to continue monitoring the patient's disease status by radiologic imaging per local standard of care (Section 8.2).

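### The protocol's follow-up provisions conflict, and a patient who stops treatment without progression may have no scheduled vital-status contact for overall survival

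*Protocol*

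**What the plan says.** - **Protocol Table 5 (long-term follow-up).** The row for patients who stop for any reason other than progression gives a 30-day safety visit, then "Clinic follow-up until toxicity resolves or until death". Imaging is left to local practice or investigator judgment. AE tracking runs to 90 days after discontinuation, or 30 days if new anticancer therapy begins. Only the row for patients who progress on study has "Survival telephone call every 12 weeks for up to 2 years". The SD/PR and CR rows have no call either, but they keep clinic visits every 8 weeks.
- **Protocol Table 4, footnote b (imaging).** "In patients who discontinue study therapy, every effort should be made to continue monitoring their disease status by radiologic imaging". How this is done is left to local practice or the investigator. The stated span is "every 8 weeks for up to 2 years until (1) the initiation of new therapy, (2) death, or (3) the end of the study".
- **Protocol Table 4, footnote c (survival calls).** "After the start of new anticancer treatment or documented disease progression by local imaging review, the patient should be contacted by telephone every 12 weeks". The calls run for at most 2 years.
- **Protocol Section 9.5.2.** "If a patient permanently discontinues study therapy, the patient should be discontinued from the study". The sentence goes on to ask for continued disease monitoring by imaging and refers to Section 8.2.
- **Synopsis, Duration of Study.** "This study consists of a 28-day screening period, treatment period, and 30-day post-treatment follow-up".
- **SAP Section 3.11.3.** OS is estimated by Kaplan-Meier, with a median and a one-year rate. Patients without a recorded death are censored at the earlier of the date last known alive and the study cutoff. SAP Table 3 likewise censors patients lost to follow-up at the date last known alive.

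**The concern.** OS needs vital status on every treated patient, whatever ended treatment. Here the provisions disagree, and one type of patient is caught by none of them. Sites working from different tables would follow the same patient for different lengths of time.

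Two things are at stake. Deaths that a telephone call would have found are lost, which costs precision. Kaplan-Meier also treats a censored patient as having the same later risk as those still followed. Patients who stop for toxicity, physician decision or non-compliance may have a different prognosis, and if they do, the OS curve is biased.

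**Working it through.** **Does any provision guarantee contact?** Take a patient who stops at month 3 for toxicity, recovers, starts no new therapy and has no further scans.

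| Provision | What it gives this patient |
|---|---|
| Table 5, non-progression row | 30-day visit; clinic follow-up until toxicity resolves; AE tracking to 90 days |
| Table 4 footnote b | Imaging if achievable under local practice; not assured |
| Table 4 footnote c | Nothing, because neither trigger (new therapy, documented progression) occurs |
| Section 9.5.2 | Leaves the study; imaging as in Section 8.2 |
| Synopsis | 30 days after treatment |

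Scheduled contact therefore ends between about month 4 (30-day visit) and month 6 (90-day AE tracking).

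**How much could it matter?** The plan gives no OS event count, power or dropout assumption that could be reproduced, so this is an illustration only. The one input taken from the documents is the 6 to 9 month median survival in protocol Section 5.1, which is background for the disease and not a design assumption. I use its midpoint, 7.5 months. The assumptions are:
- exponential survival, S(t) = 2^(-t/7.5);
- a fraction p = 0.15 or 0.25 of patients alive at month 3 stops then without progression;
- their hazard is multiplied by h afterwards;
- all of them are last contacted at month c = 4 or 6.

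Formulas:
- True 12-month OS = S(3) × [(1-p)S(9) + pS(9h)]
- Kaplan-Meier estimate with stoppers censored at c = S(3) × [(1-p)S(c-3) + pS((c-3)h)] × S(12-c)
- Patients with a missed death within 24 months = p × S(3) × [S((c-3)h) - S(21h)]

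Worked case, p = 0.25, h = 2, c = 4:
- True: 0.7579 × (0.75 × 0.4353 + 0.25 × 0.1895) = 0.283
- Estimated: 0.7579 × (0.75 × 0.9117 + 0.25 × 0.8312) × 0.4774 = 0.323
- Error: +3.9 points
- Missed deaths: 0.25 × 0.7579 × (0.8312 - 0.0206) = 15.4% of patients

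Error in 12-month OS in percentage points, with the percentage of all patients whose death within 24 months is missed in brackets:

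| Last contact, p | h = 0.5 | h = 1 | h = 1.5 | h = 2 |
|---|---|---|---|---|
| Month 4, 0.15 | -2.3 (6.5) | 0 (8.7) | +1.5 (9.3) | +2.4 (9.2) |
| Month 4, 0.25 | -3.9 (10.9) | 0 (14.6) | +2.4 (15.5) | +3.9 (15.4) |
| Month 6, 0.15 | -1.8 (5.6) | 0 (7.0) | +1.0 (6.9) | +1.6 (6.3) |
| Month 6, 0.25 | -3.0 (9.3) | 0 (11.6) | +1.7 (11.5) | +2.7 (10.5) |

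A separate simulation let stopping occur at any time. It used medians of 6 and 9 months, 10% to 40% of patients stopping, h from 0.5 to 2, and contact ending one month after stopping. The errors ran from -6.5 to +5.4 points, and were again about 0 at h = 1.

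**The case against.** The strongest reply is that Table 4 already covers these patients. Footnote b applies to everyone who discontinues therapy, and footnote c starts calls without regard to the reason for stopping. A patient who stops for toxicity at month 3, starts new therapy at month 6 and dies at month 9 is caught by footnote c. This stands. A reader of Table 5 alone might infer that these patients lose survival follow-up by design, and the documents do not support that. What they show is a conflict between provisions, with a narrower group left uncovered.

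Three further points also stand:
- Section 9.5.2 covers every permanent discontinuation, including for progression, and points back to Section 8.2. The synopsis line is equally general. Neither singles out this subgroup.
- AE tracking in the same Table 5 row runs to 90 days unless new therapy begins, so last contact need not be the 30-day visit.
- OS is secondary, descriptive and has no comparator. The primary endpoint is response and is unaffected.

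A reader might also infer that OS is biased upward. That holds only if prognosis after stopping is worse than in those still followed. Patients who stop without progression could do better, and OS would then be understated.

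The reply does not close the gap. Footnote b is a best-effort request under local practice and ends at new therapy. Footnote c needs a trigger that may never occur, or that a site may not hear of once it has released the patient.

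**Conclusion.** The point holds as an inconsistency with a real but limited gap. Table 5, Section 9.5.2 and the synopsis disagree with Table 4 footnotes b and c. A treated patient with no documented progression, no further scans and no new therapy has no scheduled vital-status contact beyond the safety and 90-day AE period, and is then censored at the date last known alive.

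Under the stated assumptions about 6% to 16% of patients have a death within 24 months that is missed, and 12-month OS is off by between -3.9 and +3.9 points. At an unchanged hazard there is no bias, only lost precision. The stopping fraction, its timing and the hazard ratio are all assumed, and the model supposes that every such patient loses contact. Where sites follow Table 4 and a trigger occurs, the loss is smaller. The case for the change does not depend on the direction of the bias. It should be made, because vital status missed during the study may not be recoverable later.

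**What to change.** 1. In Table 5 and Table 4 footnote c, apply the existing 12-weekly survival telephone contact, for up to 2 years, to every patient who ends treatment for any reason, wherever 8-weekly clinic visits are not continuing.
2. In Section 9.5.2, separate discontinuing study treatment from leaving the study, and state that survival follow-up continues unless consent for it is withdrawn.
3. Bring the synopsis study duration into line with the 2-year follow-up.

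The cost is a protocol clarification and a few extra telephone calls of a kind that sites already make. No visit, procedure or treatment rule changes.

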#### Table 5:Long-term Follow-up Schedule

Abbreviations: AE=adverse event; CR=complete remission; NA=not applicable; PR=partial response; SD=stable disease; Tx=treatment.

## 8.3. Study Procedures Descriptions

Details of the study procedures are described below. The overall schedule of assessments is provided in Table 4.

#### 8.3.1. Informed Consent

The nature of the study and its risks and benefits will be explained to the patient by the Investigator or designated study personnel as outlined in Section 16.3.

Prior to the administration of any study-specific procedures, authorized study personnel will obtain written informed consent from each potential patient. Consent should include the option to copy relevant imaging for central review by the manufacturer to enable confirmation of Investigator-determined responses.

#### 8.3.2. Eligibility Review

An eligibility review will be conducted by the Investigator at the visits specified in Table 4 using the patient inclusion criteria in Section 7.1 and exclusion criteria in Section 7.2.

#### 8.3.3. Demographics and Medical History

Patient's demographic data and medical history will be reviewed and documented at the time point(s) specified in Table 4. Tumor measurements should be collected prior to the patient's enrollment on the study. Measurements to collect should include any measurements RECIST made during the patient's previous treatment with an anti-PD-(L)1 agent.

#### 8.3.4. Prior and Concomitant Medication Review

At the time point(s) specified in Table 4, prospective patients will be asked about the medications they have taken in the last 28 days, including prescription and nonprescription medications, vitamins, and supplements.

The Investigator will record the following data on all medications used by the patient: name, dose, regimen, route of administration, start and stop dates, and the indication for use.

Prohibited medications are described in Section 8.4.2.

## 8.3.5. Infusion-Type Reactions

ALKS 4230 may be associated with infusion-type reactions. Infusion reactions should be treated at the discretion of the Investigator. The National Cancer Institute CTCAE v5.0 describes multiple types of infusion reactions:

- 1. Allergic reactions
- 2. Anaphylaxis
- 3. Cytokine release syndrome

Patients who experience Grade 3 or 4 infusion reactions should not be rechallenged with ALKS 4230.

Infusion-type reactions associated with the use of pembrolizumab should be managed in accordance with the prescribing information for pembrolizumab (Keytruda USPI).

## 8.3.6. Vital Signs and Weight

Vital signs (ie, weight, blood pressure, pulse, respiratory rate, and body temperature) will be assessed at the time point(s) specified in Table 4. Height will be measured at screening (Visit 1) only. Blood pressure, pulse, and respiratory rate will be measured after the patient has been resting in a seated or supine position for at least 5 minutes.

#### 8.3.7. Physical Examination

A physical examination will be performed at the time point(s) specified in Table 4. For cycles that do not require a full physical exam per the study flow chart, the Investigator or qualified designee will perform a directed physical exam as clinically indicated prior to study drug administration.

#### 8.3.8. 12-Lead Electrocardiogram

A 12-lead electrocardiogram (ECG) will be conducted at the time point(s) specified in Table 4.

#### 8.3.9. Eastern Cooperative Oncology Group Performance Status

The ECOG Performance Status assesses the patients' activity status and will be assessed at the time points specified in Table 4. Possible scores are 0 to 5. Descriptions of activity status are presented in Table 6.

Grade	Description
0	Normal activity. Fully active, able to carry on all pre-disease performance without restriction.
1	Symptoms, but ambulatory. Restricted in physically strenuous activity, but ambulatory and able to carry out work of a light or sedentary nature (eg, light housework, office work).
2	In bed <50% of the time. Ambulatory and capable of all self-care, but unable to carry out any work activities. Up and about more than 50% of waking hours.
3	In bed $>50\%$ of the time. Capable of only limited self-care, confined to bed or chair more than 50% of waking hours.
4	100% bedridden. Completely disabled. Cannot carry on any self-care. Totally confined to bed or chair.
5	Dead

 Table 6:
 Eastern Cooperative Oncology Group Performance Status

#### 8.3.10. Tumor Imaging and Assessment of Disease

For the purposes of this study, baseline scans must be done within 28 days before beginning treatment. In addition to a baseline scan, the first on-study imaging time point will be performed

at 6 weeks ( $\pm$  7 days) after first dose, then within 7 days prior to every second cycle thereafter, or more frequently if clinically indicated while the patient is on study.

Patients whose response converts from PD or SD to PR or from PR to CR will have a confirmatory scan for tumor assessments 6 weeks after the response-defining scan. If the patient continues on study after confirmatory scan, then the patient would receive scan per regular schedule. Thereafter, timing of tumor assessments will depend on whether or not the patient continues with study drug (see Table 5 for additional information).

Accumulating evidence indicates that a minority of patients treated with immunotherapy may derive clinical benefit despite initial evidence of PD. Allowance to continue treatment despite initial radiologic progression takes into account the observation that some patients can have a transient tumor flare in the first few months after the start of immunotherapy but with subsequent disease response. Patients will be permitted to continue on treatment beyond initial RECIST v1.1-defined PD as long as they meet the following criteria:

- Investigator-assessed clinical benefit and no rapid disease progression.
- Patient continues to meet relevant eligibility criteria, as determined by the ION and Alkermes Medical Monitors (or designee) in discussion with the Investigator.
- Stable performance status.
- Patient is tolerating study treatment.
- Treatment beyond progression will not delay an imminent intervention to prevent serious complications of disease progression (eg, CNS metastases).

The decision to continue treatment beyond initial Investigator-assessed progression should be discussed with the ION and Alkermes Medical Monitors (or designee) and documented in the study records. A follow-up scan should be performed at the next scheduled imaging evaluation 6 weeks later to determine whether there has been a decrease in the tumor size or continued PD. The assessment of clinical benefit should be balanced by clinical judgment as to whether the patient is clinically deteriorating and unlikely to receive any benefit from continued treatment. If the Investigator feels that the patient continues to achieve clinical benefit by continuing treatment, then the patient should remain on the study and continue to receive monitoring according to the Schedule of Assessments (Section 8.2), with consultation from the ION and Alkermes Medical Monitors.

Patients may receive study drug while waiting for confirmation of PD if they are clinically stable as defined by the following criteria:

- Absence of signs and symptoms (including worsening of laboratory values) indicating disease progression
- No decline in ECOG performance status
- Absence of rapid progression of disease
- Absence of progressive tumor at critical anatomical sites (eg, cord compression) requiring urgent alternative medical intervention

Table 7:Tumor Imaging/Assessment for Disease ProgressionDiseaseClinically StableClinically StableClinically Unstable

Disease	Clinically Stable		Clinically Unstable	
assessment by RECISTv1.1	Imaging	Treatment	Imaging	Treatment
1 st radiologic evidence of PD	Repeat imaging at approximately 4 to 6 weeks to confirm PD	May continue study drug at the Investigator's discretion while awaiting confirmatory scan	Repeat imaging at approximately 4 to 6 weeks to confirm PD if possible	Discontinue treatment if alternative therapy is warranted
Repeat scan confirms PD a	No additional imaging required	Discontinue treatment	No additional imaging required	NA
Repeat scan shows SD, PR, or CR	Continue regularly scheduled imaging assessments prior to every 3 rd cycle b	Continue study drug at the Investigator's discretion	Continue regularly scheduled imaging assessments prior to every 3 rd cycle b	May restart study drug if condition has improved and/or clinically stable per Investigator's discretion

Abbreviations: CR=complete remission; NA=not applicable; PD=progressive disease; PR=partial response; RECIST=Response Evaluation Criteria in Solid Tumors; SD=stable disease.

a Patients who are otherwise clinically stable may be continued on study drug, per Investigator discretion. Even if the patient remains otherwise stable, study drug will be discontinued if tumor burden increases by 25% or more following initial confirmation of progression.

b Tumor imaging/assessment will be performed at baseline, at 9 weeks, and prior to every 3rd cycle.

Response and progression for purpose of publication will be evaluated in this study using the new international criteria proposed by the revised RECIST v1.1 guideline. Changes in the largest diameter (unidimensional measurement) of the tumor lesions and the shortest diameter in the case of malignant lymph nodes will be used in the RECIST criteria.

. Clinicians are

Often with immunotherapy, tumors appear larger before they decrease in size.

encouraged to consider this possibility to avoid stopping potentially effective immunotherapy too soon.

